Randomization for a specific domain will occur when a patient is enrolled and consented into the domain. Randomization in a specific domain will be independent of previous treatment assignment, except in cases where the randomization is dependent on other domains, as specified in the domain specific protocol. We will use the word *regimen* to describe the complete set of treatments that an individual is randomised to, across each domain in which they were randomized. Within each domain, we will use block randomisation with random block sizes. Block sizes will change depending on the domain as they will include different numbers of arms. If applicable, domains will start with equal randomisation for the pilot/feasibility phase. In some domains, we will consider response adaptive randomisation after the feasibility phase, which we outline below. Patients will be randomised within a secure, online, centralized randomization tool housed at Ozmosis Research.

Stratification

In general, randomization will be stratified by site and, for domains that enrol patients across multiple states, by state. Randomization in a specific domain could also be stratified based on additional factors, as identified in the domain-specific protocol. These factors may be related to the patient but should be *stable* across time, i.e., age, sex. Due to the set-up of the randomization tool, all stratification factors will be determined at the start of the domain and will not change. Characteristics of the patient's disease that could change across the treatment period will designate the patient's *state* and alter their eligibility for domains.

Response Adaptive Randomisation

We may consider using response adaptive randomisation (RAR) for some domains, based on ethical, clinical, and statistical considerations. For statistical considerations, simulations will explore whether RAR will result in meaningfully greater efficiency and/or an expected reduction in patient harm.

RAR will initialise by enrolling a domain-specific number of participants using equal randomisation, known as the "burn-in" period for the RAR. This burn-in period will usually include all the participants in the pilot/feasibility phase, if applicable. After this burn-in period, the proportion of participants randomised to treatment will be related to the posterior probability of the treatment being optimal among the current set of treatments in the domain [2], subject to these additional rules:

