This framework differs from standard (frequentist) analyses where conclusions are based on assessing the likelihood of the observed data under a null hypothesis. This standard framework typically requires the specification of a control treatment that will be considered optimal, unless the trial data give evidence to the contrary. As our Bayesian framework is based on considering the probability that each treatment is superior compared to all other competing strategies in the domain, we do not designate a control treatment in the analysis and consider all treatments as equal until the response data are available. Based on the response data, a continuously updated ranking of the treatment regimens can be computed based on their effectiveness compared to all competing treatment regimens to which participants are currently being randomised.

Statistical interim analyses and stopping guidance

In our perpetual trial, all statistical analyses will be considered interim analyses. We will aim to undertake analyses every three months using data from all individuals who have completed data collection for the domain-specific primary outcome. Note that interim analyses may be skipped if fewer than 50 participants have been enrolled in the platform since the last analysis. Interim analyses may also be delayed for operational reasons relating to data availability. At each interim analysis, we will analyse the data for all the domain/state combinations that are currently randomizing patients and are not in their pilot/feasibility phase. The goal of these analyses is to determine whether statistical conditions (outlined below) have been met to indicate that the current treatments for the domain/state combination should be changed. Formally, the statistical rules outlined below offer guidance; final decisions regarding stopping and publication will be made by the Platform Steering Committee (PSC) and the Domain Protocol Committee (DPC) as applicable, under advisement of the DSMB. Each domain/state combination will have a pre-specified

minimum recruitment level before these statistical triggers are computed, which we can consider as a “burn-in” period for the study.

Statistical Triggers

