3. The patient is moribund and deemed unlikely to survive past 24 hours (as determined by the clinical team)
4. The patient is being transitioned to a fully palliative philosophy of care

Each state/domain combination may have additional inclusion and exclusion criteria, which will be specific in domain protocols according to domain-specific requirements.

Platform Defined States

The platform structure defines multiple mutually exclusive patient states assessed at the time of randomization in a given domain. The pre-specified states for the platform include:

1. non-intubated patients;
2. intubated patients, not on extracorporeal life support, with low normalized respiratory system elastance (<2.5 cm H₂O/ml/kg predicted body weight);
3. intubated patients, not on extracorporeal life support, with high normalized respiratory system elastance (≥ 2.5 cm H₂O/ml/kg predicted body weight);
4. patients on extracorporeal life support.

Recruitment

We will use a CONSORT 2010 flow diagram to present the recruitment numbers within each domain/state combination. In addition to the screening data explained above, the CONSORT diagram will detail the number of patients who were lost to follow-up, discontinued the intervention were included/excluded from the primary analysis.

Withdrawal/follow-up

Patients can withdraw from the platform at any time and for any reason, upon request. The reason for voluntary withdrawal from the study will not be collected. Participants who choose to withdraw from the study can choose to either discontinue the study intervention but have their outcomes recorded or withdraw from all further data collection. Individuals who discontinue the study intervention but have their outcomes recorded will be included in the intention to treat analysis. All reasons for withdrawal will be tabulated and we will record whether the patient consented to further follow-up. The numbers (with reasons) of losses to follow-up over the course of the trial will be summarised by treatment arm for each domain and within each state.

Baseline patient characteristics

We will report the following baseline characteristics for all domains:

- 1) Age
- 2) Sex
- 3) Diagnostic reason for ICU admission
- 4) Respiratory support at randomization
- 5) APACHE
- 6) SOFA
- 7) P/F ratio
- 8) Ventilatory Ratio

We may also report domain specific baseline characteristic that will be specified in the domain specific protocol.

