Individuals can transition between disease states throughout the trial but will be included in the analysis for the state that they were in when they were randomised. All outcomes will be measured from the time of randomization into the domain. Additional pilot/feasibility outcomes for domain in this phase will be defined in the domain specific protocols, harmonized where possible. All additional outcomes will be defined in the domain specific protocols and SAPs.

Analysis methods

The specific outcome model will change depending on the outcome type. Thus, this section describes the general analysis approach. Statistical modelling will adjust for variation across sites, trial time period (in 2-week intervals), the stratification variables used in randomisation (if applicable), sex, age and potential domain specific variables. Adjustments will be made using a linear predictor framework, where the link function and error distribution will change depending on outcome type. The state-specific treatment effect for the randomised treatments within a domain will be estimated on the linear predictor scale and will be additive. When pre-specified in the domain specific SAPs, baseline effects and interaction effects between treatments in different domains will be estimated in the same model. Interaction effects will only be considered when treatments for the different domains are offered concurrently. The primary analysis will not consider treatment-covariate interactions, although pre-specified secondary analyses could consider these interactions and will be specified in the domain specific analysis plans. Hierarchical modelling will be used, where pre-specified, to borrow information about the treatment effect across states.

The specific treatment effect reported will change depending on the model used. We will endeavour to present treatment effects on an interpretable scale, i.e., hazard ratios rather than log hazard ratios. The mean treatment effect and 95% high density posterior credible interval will be calculated directly from the posterior distribution of the parameter from the regression. Thus, due to the flexibility of Bayesian modelling, we hope to report functions of the parameters estimated using the linear predictor framework and ensure interpretability of our findings.

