Appendix: Inclusions for Domain-Specific Protocols/Analysis Plans

Randomization

Stratification Variables

Response Adaptive Randomisation

- Will RAR be used?
- Burn-in period

Sample Size

Feasibility study sample size

Statistical interim analyses and stopping guidance

Minimum recruitment level before statistical triggers are computed.

Probability threshold to stop for superiority

Probability threshold to stop for inferiority

Probability threshold to stop for equivalence

Minimally important clinical difference for equivalence

Futility analysis

- Will a futility analysis be used?
- Which treatments will be subject to a futility analysis?
- What probability threshold will be used?

Timing of outcome assessments

Timing of collection for all outcomes.

Adherence and protocol deviations

Definition of adherence

Definition of a protocol deviation

Analysis populations

Definition of per-protocol population

Definition of safety population

Eligibility

Domain specific inclusion/exclusion criteria

Baseline patient characteristics

Domain specific baseline characteristics to report

Outcome Definitions

Primary outcome

Secondary outcomes

Feasibility outcomes

Analysis Methods

Domain specific adjustment variables

Error distribution and link function for each outcome
Potential treatment interactions with other domains
Potential treatment covariate interactions for secondary analyses
Hierarchical model structure across states or domains
Model checking procedures
Informative priors

- Will they be used?
- How will they be defined

Subgroup analyses
Additional analyses
Safety data analyses

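### The default model omits baseline severity and respiratory support, which gives up some power, and sets 2-week period effects without requiring that they be pooled

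*SAP*

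**What the plan says.** Section 5, Analysis methods, sets the general model for all domains. It "will adjust for variation across sites, trial time period (in 2-week intervals), the stratification variables used in randomisation", followed by "sex, age and potential domain specific variables". Apart from stratification factors and domain additions, the only patient factors named are sex and age. The Appendix lists "Domain specific adjustment variables" among the items for each domain plan to fill in.

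Section 4, Baseline patient characteristics, states: "We will report the following baseline characteristics for all domains". The list includes respiratory support at randomisation, APACHE, SOFA, P/F ratio and ventilatory ratio.

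On priors, Section 5 gives half-Cauchy distributions for standard deviations and centred t distributions for coefficients, and leaves specifics to the domain SAPs. It does not say which applies to the period effects. Hierarchical modelling is described only for borrowing treatment effects across states.

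On other domains, Section 2, Randomization, makes assignment independent of earlier assignments "except in cases where the randomization is dependent on other domains". Section 5 adds: "When pre-specified in the domain specific SAPs, baseline effects and interaction effects between treatments in different domains will be estimated in the same model".

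No sample size, power or accrual rate is given. The nearest figure is in Section 2, Statistical interim analyses and stopping guidance: a three-monthly analysis may be skipped if "fewer than 50 participants have been enrolled in the platform since the last analysis".

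**The concern.** Severity measures are platform-wide prognostic factors that will already be in hand, yet the default only tabulates them. The stratification terms are unlikely to bring them in. Section 2 wants stratification factors that are stable over time and assigns changeable disease characteristics to the patient's state. The states capture part of severity (intubation, elastance, extracorporeal support), but the non-intubated and extracorporeal-support states have no further split.

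Respiratory support is the clearest case. The non-intubated state mixes patients on non-invasive ventilation with patients on oxygen or high flow. Under the ventilator-free-day definition in Section 5, the first group can score at most 28 and the second 29. The scale itself therefore depends on a recorded baseline variable that the default model omits.

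The period question is separate. Calendar time has to be adjusted for, because Section 2 allows response-adaptive allocation and the addition of arms. Two-week steps are fine-grained, about 26 a year. With no pooling required, a domain author could follow the SAP and still fit one free term per fortnight. What is at stake is later stopping triggers and, in sparse data, a treatment effect estimated too far from the null.

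Finally, where one domain's allocation depends on another domain's arm and that arm affects outcome, leaving the arm out confounds the comparison.

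**Working it through.** The SAP has no figure of its own to reproduce. The checks below rest on stated assumptions.

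**1. Patients per period.** Take the skip threshold of 50 per three months as if it were a rate. Thirteen weeks hold 13/2 = 6.5 periods, so 50/6.5 = 7.7 patients per period platform-wide (50/6 = 8.3 if a quarter is taken as 12 weeks). An even split over the four states gives 7.7/4 = 1.9. At an assumed 100, 150 or 300 patients per quarter the platform-wide figure is 15, 23 or 46.

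**2. Simulation.** Logistic model with 400 replicates per scenario. Assumptions not in the SAP: 400 patients allocated 1:1, intercept log-odds −0.85 (about 30% risk), odds ratio 0.60 conditional on severity (log 0.60 = −0.511), severity SD on the log-odds scale 1.0 or 0.6, and period SD 0.2. Power is the share of replicates with posterior probability of benefit above 0.975.

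Results at 7.7 patients per period, severity SD 1.0:

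| Model | Mean log OR (OR) | Mean SE | Power |
|---|---|---|---|
| No period terms, no severity | −0.445 (0.641) | 0.225 | 50.0% |
| Severity only | −0.528 (0.590) | 0.246 | 55.7% |
| Separate periods, near-unpenalised | −0.507 (0.603) | 0.259 | 51.2% |
| Separate periods, t prior | −0.490 (0.613) | 0.252 | 50.2% |
| Random periods | −0.446 (0.640) | 0.226 | 50.0% |
| Separate periods, t prior, plus severity | −0.592 (0.553) | 0.280 | 54.7% |
| Random periods plus severity | −0.530 (0.588) | 0.248 | 55.2% |

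**3. Cost of omitting severity.** Power difference: 55.7 − 50.0 = 5.7 points at SD 1.0, and 60.3 − 57.5 = 2.8 points at SD 0.6. The Monte Carlo SE of each figure is √(0.5 × 0.5/400) = 2.5 points. In a logistic model the gain does not show as a smaller SE, which rises from 0.225 to 0.246. The effect estimate rises by more.

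**4. Effect of separate period terms.**
- t prior: log OR 0.490/0.445 = 1.10 and SE 0.252/0.225 = 1.12.
- Near-unpenalised: 0.507/0.445 = 1.14 and 0.259/0.225 = 1.15.
- Random periods: 0.446/0.445 and 0.226/0.225, essentially no change.
- At 23 patients per period with the t prior: log OR 0.451/0.426 = 1.06.
- With a true odds ratio of 1, the one-sided false-positive rate is 3.3% with the t prior and 1.8% with random periods (nominal 2.5%, Monte Carlo SE about 0.8 points). This is too noisy to carry weight.

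**5. Both changes together.** Moving from separate t-prior periods without severity to random periods with severity raises power from 50.2% to 55.2% (SD 1.0) and from 56.8% to 59.8% (SD 0.6). Mean odds ratios are then 0.588 and 0.593 against 0.60. Adding severity while keeping separate periods gives 0.553 at SD 1.0, so the two changes belong together.

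**The case against.** A master SAP covering several phases, endpoints and states may reasonably leave prognostic covariates to its domains, and this one provides the route. Severity is therefore deferred and not barred. Randomisation also makes its omission a matter of efficiency and not of validity. Both points stand. They do not explain why measures common to all domains should be optional in each.

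Four stronger readings are tempting, and the SAP does not support them:

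- **That it fits independent 2-week terms.** It only says that it adjusts for period. Its half-Cauchy priors for standard deviations are compatible with random period effects, under which the problem almost vanishes.
- **That about 8 patients per period is the expected density.** It is the interim-skip threshold turned into a rate. True density could be higher, or lower within a domain and state.
- **That both features inflate odds ratios.** Only sparse unpooled period terms do so. Omitting severity pulls the odds ratio towards 1 (0.641 and 0.614 against 0.60). Nor does the SAP fix an odds-ratio model, since link and error distribution vary by outcome. The binary simulation does not test the ordinal ventilator-free-day outcome.
- **That cross-domain confounding is built in.** It arises only where a domain makes its randomisation dependent on another and then fails to pre-specify the term.

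There are also cautions about the remedy. Under the missing-covariate rule in Section 5, covariate missingness below 5% leads to a complete-case analysis, so new covariates could cost patients. The platform inclusion criteria rest on FiO₂ or oxygen flow and do not require a PaO₂, so P/F ratio may be missing. Adjusting for arms assigned later in other domains could itself introduce bias, because eligibility follows a changing state (Section 2) and delayed-entry domains are allowed (Section 3).

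**Conclusion.** The point holds in a limited form. The default model gives up a modest amount of power by not naming severity and respiratory support: about 3 to 6 points under the assumed severity effects, against simulation error of about 2.5 points per figure. The direction is what theory predicts, but the size depends on assumptions. The 28-versus-29 difference within the non-intubated state follows directly from the SAP's own definitions and needs no simulation.

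On calendar time, the defect is an unstated model form. If periods were separate terms with the general t prior, at about 8 patients each and in a logistic model, the log odds ratio would lie about 10% further from the null and the SE would be about 12% wider. The shift in the log odds ratio falls to about 6% at 23 patients per period and almost disappears with random effects. The adjustment for other domains needs a rule limited to assignments that precede focal randomisation and on which it depends.

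**What to change.** Amend Section 5, Analysis methods, in three places:

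1. Make one baseline severity score (APACHE or SOFA) a default main effect in every domain's primary model. In the non-intubated state, do the same for respiratory support at randomisation. Add P/F ratio where it is routinely available. For these covariates, replace the complete-case rule with imputation or joint modelling, so that no randomised patient is dropped for a missing baseline value.
2. State that 2-week period effects are partially pooled or smoothed, as a random effect or a random walk with a half-Cauchy prior on its standard deviation.
3. Include the arm assigned in another domain where randomisation in the focal domain depends on it and it was assigned before focal randomisation. State that arms assigned later are not adjusted for.

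The cost is SAP wording, a few model terms and some extra work on missing baseline values. No new data collection is needed.

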Outcomes are collected in the iCORE, INDEX or I2 registries or in platform CRFs for sites not participating in a registry. Specific additional outcomes and their timing will be addressed in the domain specific protocols/SAPs.

Section 3: Statistical Principles

Statistical Reporting

All inferential statistics will be undertaken in a Bayesian framework [3]. Thus, when inferential statistics are used, we will report the posterior mean, median and 95% highest density credible interval for the parameter of interest. The primary analysis and pre-specified secondary analyses will also report the posterior probability of superiority (or its complement, inferiority). We will not report p-values and will not adjust for multiplicity as analyses are undertaken in a Bayesian framework [4]. Comprehensive simulations will be undertaken when a domain is added to ensure the proposed trial has good operating characteristics within each state.

Adherence and protocol deviations

Adherence and protocol deviations will be defined separately for each domain in the domain specific protocol and SAP. Adherence and protocol deviations will be presented using descriptive statistics by arm in each domain and state combination.

Analysis populations

Intention to Treat Population: All individuals who are randomised and meet the inclusion criteria and consent for the domain and state in which we are conducting the analysis. Individuals will be included in the intention to treat analysis irrespective of whether they received the treatment to which they were randomised. We may define some *delayed entry* domains, where individuals are only eligible for this domain after receiving other treatments, i.e., domains governing treatment in recovery. The intention to treat population for these domains will, similarly, include all individuals who meet the inclusion criteria and are consented for the domain. Thus, in delayed entry domains, the inclusion criteria will explicitly indicate the treatment and disease trajectory that must be followed to be eligible for delayed entry.

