If the level of missingness for the covariates is below 5%, we will undertake a complete case analysis using the observed data. If the level of missingness exceeds 5%, we will evaluate whether a complete case analysis is suitable by investigating the baseline characteristics between individuals with and without the missing outcome. Using this information, expert opinion will be leveraged to determine whether a complete case analysis could be appropriate in this setting. If a complete case analysis is not suitable, we will undertake a joint Bayesian analysis of the missingness mechanism and outcome model. This joint analysis will be the primary analysis. We will also undertake a secondary complete case analysis to explore any differences.

Outcomes

In general, we will not jointly model or impute missing outcomes. Thus, if the level of missingness for a specific outcome exceeds 5%, we will investigate the baseline prognostic characteristics and treatment assignment of individuals with and without the missing outcome. If substantial differences are observed, we will report descriptive statistics for this outcome and report the

reasons that individuals were lost to follow up. If we are analysing a composite outcome, we will consider joint modelling of the missingness mechanism and specific elements that contribute to the outcome. We would jointly model the missingness for the outcomes that contribute to the composite outcome, if the missingness for that specific element exceeds 5%, and the outcome.

Additional analyses

Additional analyses will be defined in the domain specific protocols and may include joint modelling of different outcomes. Inferential statistics will follow the general principles outlined in this SAP.

Harms

Safety outcomes will be specified in the domain specific protocols. Unless specifically specified in the domain specific SAP, inferential analyses will not be used for safety data. Descriptive statistics detailing the number and proportion of adverse events observed in each category will be provided. The safety population and the safety data definitions will be defined in the domain specific protocols.

Statistical software

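### The covariate missing-data rule checks the wrong patients above 5%, and below 5% drops randomised patients under a threshold whose unit is not stated

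*SAP*

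**What the plan says.** The rule is in the SAP, Section 5, Missing data, under Covariates. It has two branches.

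- **Below 5%:** "If the level of missingness for the covariates is below 5%, we will undertake a complete case analysis using the observed data". No check and no sensitivity analysis are attached to this branch.
- **Above 5%:** suitability of complete case is assessed by "investigating the baseline characteristics between individuals with and without the missing outcome", after which "expert opinion will be leveraged to determine whether a complete case analysis could be appropriate in this setting". Then: "If a complete case analysis is not suitable, we will undertake a joint Bayesian analysis of the missingness mechanism and outcome model". In that event the joint analysis is primary and complete case is secondary.

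The next paragraph, Outcomes, has its own 5% rule with a similar check: "we will investigate the baseline prognostic characteristics and treatment assignment of individuals with and without the missing outcome".

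Under Analysis methods, the model adjusts for site, trial time period in 2-week intervals, and "the stratification variables used in randomisation (if applicable), sex, age and potential domain specific variables". Section 3 (Analysis populations) defines the intention-to-treat population as randomised individuals who meet the inclusion criteria and consent for the domain and state, and adds: "Individuals will be included in the intention to treat analysis irrespective of whether they received the treatment to which they were randomised".

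**The concern.** A complete-case analysis for covariates removes patients with at least one missing adjustment variable, many of whom may have an observed outcome. To judge whether this is acceptable, one must look at the removed patients. The SAP instead splits patients by whether the outcome is missing. That table can look reassuring while the patients lost for a missing covariate differ markedly from the rest, or look alarming when they do not.

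The check is also the gate between two primary analyses. If it points the wrong way, or is uninformative, the choice falls to expert opinion with no stated criterion.

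Below 5% there is no check at all. Patients with observed outcomes leave the primary model, although the plan already accepts, above 5%, a method that could retain them. How many can leave automatically depends on whether the 5% is per covariate or joint, and the text does not say. Two analysts could follow the same paragraph and reach different primary analyses. Under Statistical interim analyses, analyses are intended every three months, and a treatment stopped on a confirmed trigger cannot be reinstated, so the analysis set should not be open to interpretation.

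**Working it through.** **1. Which patients does each check examine?**

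| Paragraph | Patients removed by complete case | Groups compared |
|---|---|---|
| Covariates | those missing a covariate | missing outcome vs not |
| Outcomes | those missing the outcome | missing outcome vs not |

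The groups match in the second row and not in the first. The wording was probably carried over from the Outcomes paragraph, where it fits. The Outcomes version also looks at treatment assignment; the Covariates version does not.

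**2. Is the gap handed to the domain documents?** The SAP appendix lists what domain protocols and analysis plans must specify. It asks for domain-specific adjustment variables but has no item for missing data. A domain can therefore add covariates without being prompted to repair this rule.

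**3. Size of the automatic loss.** The SAP states no expected loss, so there is no figure of its own to reproduce.

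Inputs:
- Threshold: 5% (SAP, Covariates).
- Number *k* of covariates with missing values, and rate *m* for each: not given, so assumed. Range shown: *k* = 1 to 6 and *m* = 1% to 4.9%.

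Joint reading (share of patients missing any covariate): automatic loss is below 5% for every *k*.

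Per-covariate reading, with *m* just under the limit:
- full overlap: loss = *m*
- independent: loss = 1 − (1 − *m*)^*k*
- no overlap: loss = *k* × *m*

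For *k* = 4 and *m* = 4.9%:
- full overlap: 4.9%
- independent: 1 − 0.951^4 = 1 − 0.818 = 18.2%
- no overlap: 4 × 4.9% = 19.6%

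Other independent cases:

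| *m* | *k* | Loss |
|---|---|---|
| 4.9% | 1 | 4.9% |
| 4.9% | 2 | 9.6% |
| 4.9% | 3 | 14.0% |
| 4.9% | 5 | 22.2% |
| 4.9% | 6 | 26.0% |
| 3% | 4 | 11.5% |
| 2% | 4 | 7.8% |
| 1% | 4 | 3.9% |

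**4. Which covariates can be missing?** Site, calendar period and stratification factors are needed to randomise or follow from the randomisation date. Age is an inclusion criterion. Sex should very rarely be missing. Losses would therefore come almost wholly from domain-specific covariates, whose number this document leaves open.

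**5. Boundary.** The branches are below 5% and exceeding 5%, so exactly 5% falls in neither.

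**The case against.** **The large loss rests on the weaker reading.** The rule speaks of covariates in the plural, whereas the Outcomes paragraph refers to one specific outcome or element when it means a single variable. That contrast favours a joint reading, under which automatic loss stays below 5%. This stands against treating 18.2% as an expected loss; it does not make the unit explicit.

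**The plan has a fallback.** Above 5% a joint Bayesian model can become primary, with complete case secondary, which is close to what is recommended here. This stands and should be credited. It does not cure the faulty check, because that check decides whether the fallback is used, and the fallback is not available below 5%.

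**Complete case for a small share of missing baseline values is an accepted method.** Missingness that arises before assignment does not by itself bias a randomised comparison. This also stands: no bias is claimed. The argument is that observed outcomes are discarded when a cheap method would keep them.

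**Two stronger readings are tempting.** A reader might infer that the rule contradicts the intention-to-treat definition. The quoted sentence concerns receipt of the allocated treatment, not completeness of covariates, and Section 4 (Recruitment) already plans to report who was included in or excluded from the primary analysis. The rule narrows the analysed set within that population, which is a weaker point than contradiction. A reader might also turn the loss into a fall in power. The SAP states no power and no fixed sample size, and stopping follows posterior triggers, so such a figure would not describe this trial. Lost information would mainly delay a trigger.

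**Conclusion.** The concern holds in three parts.

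- **The check above 5% is wrong as written.** This rests on the text alone and on no numerical assumption. Because it helps choose the primary analysis, it is more than a clerical slip.
- **Automatic deletion below 5% is avoidable.** Retaining these patients fits methods that the SAP already accepts.
- **The unit of the 5% threshold is undefined.** Under a joint reading the consequence is small, below 5%. Under a per-covariate reading, the four-covariate illustration spans 4.9% to 19.6%. Its 18.2% value needs three assumptions together: a per-covariate threshold, four domain-specific covariates each just under the limit, and independent missingness. None is stated in the SAP.

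The rule should be corrected. The case for doing so does not depend on the size of the illustrated loss.

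**What to change.** Reword the Covariates paragraph of the SAP:

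1. Keep every randomised patient with an observed outcome in the primary model, whatever the level of covariate missingness. Either impute missing baseline covariates from baseline data only (for example mean or mode with a missing indicator), or model them within the Bayesian model, extending the plan's own joint-model fallback to any level of missingness.
2. Make complete case the sensitivity analysis throughout.
3. If a threshold is kept, define it as the share of patients missing any model covariate, assign exactly 5% to one branch, and base the check on patients with and without missing covariates, by arm.
4. Add a missing-covariate item to the appendix list for domain documents, so that each domain that adds adjustment variables names its method.

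The cost is SAP wording, a little more modelling work and some code. No new data are needed.
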